3. STUDY DESIGN

This is a Phase II a, prospective study comprising of 60 subjects referred to Liverpool Hospital and Sydney Southwest Private Hospital who have paired FFR assessments. To achieve this number, assuming a dropout rate of 25%, approximately 80 subjects will be approached. These subjects will be undergoing investigation for **symptomatic CHD**. Once consent has been obtained and the subject has met all the inclusion criteria without exclusions, they will be included in the study. The study is a randomised, placebo controlled trial at a randomisation rate of 1:1.

The primary endpoint will be a 20% reduction in the rate of FFR <0.80 in subjects planned to undergo staged PCI at 3 months among those randomly assigned to ACAC therapy. That is a difference of 6 or more in the ACAC group who had an FFR <0.80 at onset will have a FFR ≥0.80 at 3 months than in control group.

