4.3 Recruitment

Two centre's will participate, enrolling subjects until 60 have completed study participation defined as completing paired FFR assessments per protocol. Subjects meeting the diagnostic criteria for myocardial ischemia or a recent acute coronary syndrome whose cardiologist recommends angiography will be eligible.

Subjects presenting to the study centre/s will be invited to participate. All eligible subjects who are willing to participate will be given the opportunity to ask questions, and will be informed about the study before signing consent. Subject characteristics will be registered on a case report form that contains basic demographics and clinical characteristics age, sex, medical history, smoking and drinking habits, concomitant medications and current symptoms. In addition, a physical examination will be performed by the Investigator or sub-investigators including height, weight and vital signs.

Subjects who fail the inclusion/exclusion criteria will be informed that they are not eligible for inclusion into the study and will be treated by the Investigator as per standard clinical practice.

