7.1.3 Visit 3 – End of Treatment (Day 90 ± 21)

At this visit the Subject will be asked to report on current symptoms, changes to concomitant medications, and adverse events. A blood sample will be collected for laboratory tests. Subject will undergo a physical examination. The following assessments will also be performed:

- FBC, ESR and EUC
- LFT and Lipid Studies
- CK-MB, high sensitivity Troponin T
- High sensitivity CRP
- *Chlamydophila pneumoniae* macrophage cultures
- *C. pneumoniae* titer measurement
- *C. pneumoniae* DNA detection using LAMP
- Symptomatology record
- Physical examination
- Vital Signs
- ECG
- Angiogram
- Fractional Flow Reserve Study and pressure/flow measurements
- IVUS and OCT of culprit and non-culprit arteries (sub-study)
- Functional status – New York Heart Association Class

The Subject will be required to return all unused medication, and all used empty packaging for assessment of compliance. Subjects will also be required to return diaries for review and collection.

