7.2.1.5 Fractional Flow Reserve (FFR) Study

The results will assess the physiological effect of arterial stenosis.

Fractional Flow Reserve study is a guide wire based procedure to measure changes in blood pressure and flow across non-critical lesions in the coronary arteries performed at the time of a diagnostic or interventional coronary procedures. The results will assess the degree of arterial stenosis. This is a common clinically indicated procedure, which will be performed at

baseline and at Visit 3. Additional measurements of coronary flow as measured with the FFR pressure/flow guidewire will be recorded in the culprit and non-culprit artery at the time of FFR measurement.

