9. WITHDRAWALS AND DEFAULTERS

Subjects may be withdrawn from study medication for the following reasons:

- Determined to be necessary as per investigator, including:
 - Due to AE or SAE
 - Development of any exclusion criteria may be cause for discontinuation
 - Treatment with prohibited medications
 - Female participants fall pregnant or female partners of male participants fall pregnant
 - Subject lost to follow up (does not complete all Study visits and Study staff have failed to make contact with the subject nor arrange a successful visit for a period of 1 month past a scheduled Study visit).
 - If, in the investigators opinion continuation in the study would be detrimental to the subjects well-being

- Subjects are free to withdraw consent at any time.

In all cases the reason for withdrawal, if given, must be recorded in the Case Report Form and in the subject's medical records. The subject must be followed up to establish whether the reason was an adverse event, and if so, this must be reported in accordance with the procedures in section 8 Adverse Events.

Every effort will be made to follow up subjects who withdraw or are withdrawn from the study. All subjects withdrawn or who choose to withdraw consent will be asked to return to the study site to undergo final EOT study procedures, or as far as possible, all safety examinations scheduled for the final EOT visit for all subjects who taken at least one dose of the study drug/s. This is especially important for those subjects who withdraw due to AEs or SAEs, in order to allow for collection of detailed safety data in accordance with the procedures in section 8 Adverse Events. These subjects should be given appropriate care under medical supervision until the symptoms of any AE resolve, or the subject's condition becomes stable. Subjects may then be contacted at the end of the study for final safety monitoring procedures.

While primary analysis will be of all consenting subjects, a secondary 'on-treatment' analysis will be performed on subjects who remain compliant at the end of the 90-day endpoint.

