11. STATISTICAL PROCEDURES

11.1 *Analysis Variables*

Analysis of efficacy will be performed according to intention-to-treat method and include all subjects who received the combination antibiotic therapy. However as the primary efficacy analysis is of subjects with paired FFR assessments, only such subjects will be included in the primary analysis. All other subjects will be included in secondary analyses. Numerical data will be presented as mean \pm SD for normally distributed variables and as median with interquartile range for non-normally distributed data. Non-normally distributed data will be log-transformed (e.g. CRP levels) before being used for comparisons. Significant changes in subjects' arterial flow, clinical symptoms and biochemical variables over time compared with that baseline will be assessed using an analysis of covariance. Differences between treatment and control groups in the occurrence of FFR \geq 80 will be assessed using Fisher's exact test. All tests will be 2-tailed with a 5% significance level.

11.2 *Interim Analysis*

A DSMB directed interim analysis is planned when 60 paired FFR data are available. At this time point, the trial would declare the combination therapy as effective if the p value is less than 0.05. However, the trial might still continue to collect extra data to accurately characterise side effects as advised by the DSMB.

11.3 *Sample Size Justification*

This is a feasibility study designed to provide preliminary observations and generate hypothesis for future studies. The sample size of 60 subjects with paired FFR was not defined on the basis of a clinical endpoint hypothesis but rather to provide information about antibiotic combination therapy efficacy and safety. The sample size required is established by assessment of the minimum number of subjects needed to provide reliable and non-trivial results. The sample size is in the range of the intervention group in the azithromycin clinical trial of subjects with CAD (n=60).

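### A subject whose study lesion is treated by PCI before Visit 3 and has no repeat FFR leaves the primary analysis and is made up by another; no endpoint rule covers early PCI

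*Combined protocol and SAP*

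**What the plan says.** The responder rule is in Section 3. It counts subjects "who had an FFR <0.80 at onset will have a FFR ≥0.80 at 3 months", "in subjects planned to undergo staged PCI at 3 months". Section 11.1 compares the arms on this outcome by Fisher's exact test, two-sided at 5%.

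On who is analysed, Section 11.1 says of subjects with paired FFR that "only such subjects will be included in the primary analysis"; all others go to secondary analyses. Section 4.3 has the centres "enrolling subjects until 60 have completed study participation defined as completing paired FFR assessments per protocol". Section 9 differs: "While primary analysis will be of all consenting subjects". It also says that withdrawn subjects "will be asked to return to the study site to undergo final EOT study procedures", or, failing that, as many of the safety examinations as possible.

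On the measurement, Visit 3 (Section 7.1.3) lists "Fractional Flow Reserve Study and pressure/flow measurements" without an exception for a treated lesion and without fixing the order relative to the staged PCI. Section 7.2.1.5 describes FFR as taken "across non-critical lesions in the coronary arteries".

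No section says what happens when the qualifying lesion is revascularised between baseline and Visit 3. Three provisions come near. Exclusion criterion 2 requires a non-culprit lesion fit for planned staged PCI. Section 9 lets the later development of an exclusion criterion be a ground for stopping study medication. Section 4.4 allows withdrawals and late exclusions to be replaced, referring to a Section 9.2 that the protocol does not contain.

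**The concern.** Every subject enters with a lesion of FFR 0.80 or below that is already judged suitable for staged PCI, and the trial needs that lesion left alone for about 90 days in symptomatic patients. PCI ahead of schedule is foreseeable. It may mean that symptoms worsened, or only that a catheter laboratory slot came free; the plan does not separate the two.

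If FFR is not repeated, Sections 11.1 and 4.3 together remove the subject and recruit until the pair is made up. The analysed groups are then selected by something that happened after randomisation and may depend on treatment. A treatment that leads to more early PCI through worsening would lose its worst subjects from its own denominator.

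If FFR is repeated after a stent, the literal Section 3 rule has nothing to stop a value of 0.80 or more from being read as response, although it would measure the stent. An analyst would have to decide, possibly with the data in hand.

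**Working it through.** **The plan's own figures.** 60/(1 − 0.25) = 80 subjects approached, and 0.20 × 30 per arm = 6 subjects difference. Both match Section 3. No power, control response rate or early-PCI rate is given, so everything below rests on assumed rates.

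**Inputs.** 60 pairs at 1:1, taken as 30 per arm (Sections 3 and 4.3); two-sided Fisher's exact test at 0.05 (Section 11.1). Assumed: true response r of 30% ACAC v 10% placebo, the 20-point difference of Section 3; early-PCI rate e of 3% or 10% per arm; post-stent FFR always at least 0.80.

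**Response probability per arm under each handling**

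- A, scored as response, PCI unrelated to response: r(1 − e) + e
- B, scored as non-response, PCI unrelated to response: r(1 − e)
- C, removed and made up to 30, PCI unrelated to response: r
- D, removed and made up to 30, stented subjects would all have been non-responders: r/(1 − e)

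Power is the sum, over all pairs of counts (a, b) from 0 to 30 with Fisher p < 0.05, of Bin(a; 30, p_ACAC) × Bin(b; 30, p_placebo). With e = 0 it is 37%.

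| e, ACAC / placebo | A | B | C | D |
|---|---|---|---|---|
| 3% / 3% | 33% | 35% | 37% | 39% |
| 10% / 10% | 25% | 31% | 37% | 44% |
| 3% / 10% | 14% | 39% | 37% | 35% |
| 10% / 3% | 49% | 28% | 37% | 47% |

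Example for D at 10% / 3%: 0.30/0.90 = 33.3% and 0.10/0.97 = 10.3%, an apparent difference of 23.0 points against a true 20. Under D's assumption, keeping the subjects as non-responders returns r itself, hence 37%. So B loses power if early PCI is a scheduling matter, and is exact if it marks a lesion that would not have responded.

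**No effect (10% v 10%).** Two-sided rejection stays below 5% in all these cases. The highest is 4.6%, under A with 3% in one arm and 10% in the other; B gives at most 0.9%.

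**One subject.** If one early-stented subject exists and is scored as response instead of non-response, with the other 59 binomial, the verdict at p < 0.05 changes with these probabilities:

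| True response, ACAC v placebo | Subject in ACAC | Subject in placebo |
|---|---|---|
| 30% v 10% | 11% | 15% |
| 40% v 20% | 9% | 11% |
| 10% v 10% | about 1% | about 1% |

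Near the boundary, 12/30 v 5/30 has p = 0.084 and 13/30 v 5/30 has p = 0.047. At 9/30 v 3/30 (p = 0.104), one result with Section 3's difference of 6, one extra responder changes nothing: 10 v 3 gives p = 0.058 and 9 v 4 gives p = 0.209.

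**The case against.** The text leans towards an untreated lesion. The primary objective (Section 2.1) concerns non-critical lesions in non-culprit arteries, Section 3 speaks of subjects still awaiting staged PCI, Section 4.3 wants pairs obtained per protocol, and Section 7.2.1.5 again names non-critical lesions. For a stent result to be scored as response, the lesion must be treated early, an invasive FFR must be repeated in it, and an analyst must accept it as the paired value. Section 9 only asks withdrawn subjects back and accepts safety examinations instead. This stands: that route is possible, not likely.

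A stented subject arguably meets exclusion 2, so could be discontinued under Section 9 and replaced under Section 4.4. Those provisions are permissive, and neither says how to score the subject. Replacement is also the removal objected to here.

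The paired-FFR restriction and its conflict with Section 9 affect any missing FFR, whatever the cause. That is right; early PCI is the case where the cause is most likely to be tied to outcome.

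Non-response scoring is not neutral: it counts a PCI moved for convenience as failure. Making exclusion primary and non-response the sensitivity analysis is also defensible. What is hard to defend is leaving the choice open.

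Finally, Section 11.3 calls this a hypothesis-generating feasibility study. That limits the consequence, but Section 11.2 still declares the therapy effective at p < 0.05 with 60 pairs.

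**Conclusion.** The point holds as a gap in the endpoint and analysis-set rules. Its firm part follows from the stated rules: with no repeat FFR, Sections 11.1 and 4.3 remove and make up a randomised subject because of an event after randomisation, and Section 9 contradicts this without resolving it. The post-stent response is the weaker part; the literal rule permits it and the surrounding text points away from it.

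A reader might infer that the trial intends to count stents as drug responses, or that the gap favours ACAC. The documents support neither. Early PCI scored as response in placebo hides an effect and in ACAC adds to one, and no early-PCI rate is given for either arm. Nor do the calculations show a false-positive rate above 5% in the cases examined. The widest contrast, 14% v 39% power, needs an imbalance of 3% v 10% between arms for which the documents give no basis.

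Under the assumed rates, removal moves power from 37% to between 35% and 47% if stented subjects would not have responded, and not at all if early PCI is unrelated to response. Severity is low to moderate, with medium confidence.

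**What to change.** - In Sections 3 and 11.1, define response as FFR of at least 0.80 at Visit 3, measured before the staged PCI, in the qualifying lesion (the non-culprit lesion or the single intermediate lesion), with no revascularisation of that lesion since baseline.
- Score earlier revascularisation of that lesion as non-response, whether or not FFR is repeated. Keep the subject in the primary analysis, count the subject towards the 60, and do not replace.
- Align Sections 4.3, 4.4 and 9 with this set.
- Add a sensitivity analysis that excludes these subjects, to cover PCI brought forward for logistical reasons.
- Leave post-stent FFR and QCA values of that lesion out of the continuous drug-effect analyses.
- Report early revascularisation of the study lesion by arm, with the reason.

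This costs a few sentences and one CRF field, with no extra subjects or procedures. The statistical price arises when PCI is moved for reasons unrelated to response. From 30% v 10% and 37% power, equal 3% early PCI gives 29.1% v 9.7% (0.97 × each rate) and 35% power; equal 10% gives 27% v 9% and 31%; 10% in ACAC with 3% in placebo gives 28%. The rule should be fixed before unblinding.

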4. SELECTION OF STUDY POPULATION

4.1 Inclusion Criteria

The subject must meet all of the following criteria to be eligible for inclusion in the study:

1. Males and females (without childbearing potential as evidenced by hysterectomy, tubal ligation or at least one year post-menopause) aged 18 to 80 years, inclusive.
2. Ability to provide written informed consent to participate in the study.
3. Subjects with documented recent acute coronary syndrome (ACS) or evidence of myocardial ischemia.
4. Subjects who have a culprit lesion suitable for PCI, and a non-critical lesion in another vessel suitable for staged PCI with an FFR of ≤ 0.80 , for subjects undergoing diagnostic angiography and FFR without ad hoc PCI. Or subjects who have a single non-critical culprit lesion of intermediate severity with a clinically indicated FFR ≤ 0.80 which is suitable for staged PCI.
5. No serious co-morbidities, which might interfere with the subject's ability to enter the study.
6. Able to communicate effectively with the study team and to comply with the protocol.

4.2 **Exclusion Criteria**

The subject must be excluded for any of the following reasons:

1. Females that are of child bearing potential
2. Subjects without a non-culprit lesion considered appropriate to plan a staged PCI.
3. Clinically significant haematologic, hepatic, metabolic, renal, rheumatologic, anaphylactic reactions, neurological or psychiatric disease
4. Clinical evidence of any other disease, which might interfere with the subject's ability to enter the trial.
5. Concomitant administration of medications that may interfere with treatment as assessed by the Investigator, including allergy to any component of the therapy.
6. Concomitant administration of any medication prohibited for use during this study (e.g. colchicine)
7. Male subjects consuming greater than 60g alcohol per day, or female subjects consuming greater than 40g alcohol per day.
8. Evidence of any recent history of, or current recreational drug abuse
9. Serious adverse reaction or hypersensitivity to therapeutic drugs.
10. Unable and to comply with the study requirements.
11. Subjects who have been involved in an experimental drug protocol within the past four weeks.

A list of subjects screened but deemed ineligible will be maintained indicating reason(s) for exclusion.

If a subject becomes pregnant during the course of the study, they will be immediately withdrawn and treated in the way least likely to harm both subject and foetus.

4.3 Recruitment

Two centre's will participate, enrolling subjects until 60 have completed study participation defined as completing paired FFR assessments per protocol. Subjects meeting the diagnostic criteria for myocardial ischemia or a recent acute coronary syndrome whose cardiologist recommends angiography will be eligible.

Subjects presenting to the study centre/s will be invited to participate. All eligible subjects who are willing to participate will be given the opportunity to ask questions, and will be informed about the study before signing consent. Subject characteristics will be registered on a case report form that contains basic demographics and clinical characteristics age, sex, medical history, smoking and drinking habits, concomitant medications and current symptoms. In addition, a physical examination will be performed by the Investigator or sub-investigators including height, weight and vital signs.

Subjects who fail the inclusion/exclusion criteria will be informed that they are not eligible for inclusion into the study and will be treated by the Investigator as per standard clinical practice.

4.4 Number of Subjects

A total of 60 subjects will complete study participation. Withdrawn and delayed exclusions may be replaced, see Section 9.2.

4.5 Randomisation and Randomisation Schedule

For the purposes of this study, participants will be randomised at screening visit.

Subjects recruited into the study who are then deemed eligible for Randomisation at Screening Visit will be randomised in a double-blinded 1:1 manner, either to active study medication or matching placebo.

Randomisation will be performed centrally by CDD. Sites will need to contact CDD to randomise study participants. CDD will be responsible for allocation of study medication based on the randomisation number. Randomisation numbers will be given out to site over the phone and confirmed electronically via signed, emailed randomisation confirmation sheet.

CDD is not a clinical site for the conduct of the trial so study investigators involved in any study participant recruitment, assessment and eventual follow-up will remain blinded to the medication therapy assignment.

Investigators/Sub-Investigators will be instructed to contact CDD on the number below;

CDD
Research Department
[name] then dial '2' for the Research Department

4.6 Blinding Procedures

In order to eliminate a placebo effect, the subject and clinical study investigators / staff will be blinded to the allocation of treatment in a double-blinded fashion.

Unblinded CDD staff will allocate subject numbers according to the treatment arm to which the subject is assigned. Medication will be dispensed by site staff as allocated by subject numbers provided by CDD.

5. STUDY PRODUCT

5.1 Dosage Schedule

The treatment will be administered as 50mg capsules of doxycycline, 250mg capsules of azithromycin and 150mg of rifabutin twice daily (morning and evening). The total number of capsules taken is 3 capsules a day in the first week then 6 capsules a day to be taken after food, with plenty of fluids, until the end of dosing period.

The treatment is to be on a dose escalation schedule, taken as per the following schedule:

Week 1 (Day 1 to Day 7)

Time	Doxycycline	Azithromycin	Rifabutin
Breakfast	50mg	250mg	150mg
Dinner			

Week 2 until EOT (Day 8 to Day 90)

Time	Doxycycline	Azithromycin	Rifabutin
Breakfast	50mg	250mg	150mg
Dinner	50mg	250mg	150mg

5.2 Supplies and Accountability

The Sponsor will be responsible for supplying the Investigators/institutions with the study drug. The Sponsor will not supply an Investigator/institution with the study drug until the Sponsor obtains all required documentation from the HREC and regulatory authorities. The Sponsor will ensure timely delivery of investigational product(s) to the Investigator(s) and maintain records that document shipment, receipt, disposition, return, and destruction of the study drug.

The Principal Investigator is responsible for study drug accountability, reconciliation, and record maintenance at his/her site. The Principal Investigator or designated, trained study site personnel will document all aspects of drug receipt, inventory, dispensing, return, reconciliation, and shipment.

All study medication must be kept in a locked area with access restricted to designated study site personnel. At each visit, a supply of study medication sufficient to last until the next clinic visit will be dispensed (plus a small additional quantity to account for the visit window). A list of the exact supply of study treatment dispensed to each Subject at each visit will be included on the Investigational Product Accountability Log that will need to be completed at each study visit. Used and unused product will be returned by the Subject to the clinic in the packaging in which it was provided to the Subject. The Investigator or delegated staff will reconcile all study units with those recorded as being dispensed and account for any inconsistencies in writing in the Investigational Product Accountability Log or similar document maintained in the Investigator study file.

At the conclusion of the study, all unused medication and all medication containers will be returned to the Sponsor. The Sponsor will ensure that a final report of drug accountability is prepared and that unused medications are appropriately destroyed.

5.3 *Packaging and Labeling*

Study medications will be packed and supplied by the Sponsor. Medication will be labelled with dosing instructions, the protocol number, subject number and will indicate that the supplies are for clinical trial use only. Study medications will be dispensed in study specific bottles, appropriately labeled. Packs must only be allocated to the subject whose number is borne on that pack. Subjects will be asked to return all partly used packs at each clinic visit. Further supply will be prescribed at visit suitable for the treatment period.

5.4 *Compliance*

Compliance will be assessed by capsule counts conducted by the Investigator or delegated staff at each visit. Compliance will be calculated as a percentage (%) of expected and the value will be entered on the appropriate page of the CRF at each study visit. Secondary 'on treatment' analyses will be performed. Participants will be deemed 'non-compliant' if compliance percentage falls below 80%, at which point, study staff are required to re-educate the participant on study medication dosing.

